8.2 Subject Identification and Replacement of Subjects

Each subject will be assigned a unique subject identifier. This unique identifier will be on all case report form (CRF) pages. Subjects who do not receive at least one dose of tipifarnib will be replaced.

8.3 Assignment to Treatment Groups

All eligible subjects will be randomized to receive tipifarnib administered according to one of the following dose regimens:

- Regimen 1: 600 mg bid for 7 days on Days 1-7 in 28 day cycles (i.e. 1 week on / 3 weeks off).
- Regimen 2: 300 mg bid for 21 days on Days 1-21 in 28 day cycles (i.e. 3 weeks on / 1 week off).

8.4 Removal of Subjects from Treatment or Assessment

Subjects may withdraw their consent to participate in this study at any time without prejudice. The Investigator must withdraw from the study any subject who requests to be withdrawn. A subject's participation in the study may also be discontinued at any time at the discretion of the Investigator and in accordance with his/her clinical judgment. Every effort should be made to complete, whenever possible, the tests and evaluations listed for the End of Treatment visit. The Sponsor must be notified of all subject withdrawals as soon as possible. The Sponsor also reserves the right to discontinue the study at any time for either clinical research or administrative reasons and to discontinue participation by an individual Investigator or site for poor enrollment or noncompliance.

Overall, the reasons for which the Investigator or Kura Oncology may withdraw a subject from study treatment include, but are not limited to, the following:

- Subject experiences disease progression
- Subject experiences unacceptable toxicity
- Subject requires more than 2 dose reductions
- Subject experiences toxicity that is deemed by the Investigator to be no longer safe for the subject to continue therapy
- Subject requests to withdraw from the study treatment
- Subject requires or has taken medication prohibited by the protocol
- Subject is unwilling or unable to comply with the study requirements
- Subject withdraws consent to collect health information
- Subject was erroneously admitted into the study or does not meet entry criteria
- Subject is lost to follow-up
- Subject becomes pregnant

Subjects will return for an End of Treatment visit within approximately 30 days after the last administration of the study drug (or sooner if another anticancer therapy is to be initiated). If a subject fails to return for scheduled visits, a documented effort must be made to determine the reason. If the subject cannot be reached by telephone after 2 attempts, a certified letter should be

sent to the subject (or the subject's legally authorized representative, if appropriate) requesting contact with the Investigator. This information should be recorded in the study records.

Prior to enrollment into the study, the Investigator or designee must explain to each subject, that the subject's protected health information obtained during the study may be shared with the study Sponsor, regulatory agencies, and Institutional Review Board/Independent Ethics Committee (IRB/IEC) in order to analyze and evaluate study results. It is the Investigator's (or designee's) responsibility to obtain written permission to use protected health information per country-specific regulations, such as Health Information Portability and Accountability Act (HIPAA) in the United States, from each subject, or if appropriate, the subject's legally authorized representative. If permission to use protected health information is withdrawn, it is the Investigator's responsibility to obtain a written request, to ensure that no further data will be collected from the subject and the subject will be removed from the study.

8.5 Premature Discontinuation of the Trial

This study may be discontinued prematurely in the event of any of the following:

- New information leading to a judgment of unfavorable risk-benefit of tipifarnib becomes available, e.g. evidence of inefficacy of tipifarnib in subjects with very low, low or INT risk MDS, occurrence of significant previously unknown adverse reactions or unexpectedly high intensity or incidence of previously known adverse reactions, or other unfavorable safety findings in the very low, low or INT risk MDS patient population. Evidence of inefficacy may arise from this study or from other trials; unfavorable safety findings may arise from clinical or non-clinical examinations, e.g. toxicology.
- Sponsor's decision that continuation of the study is unjustifiable for medical or ethical reasons.
- Poor enrollment of subjects making completion of the study within an acceptable time frame unlikely.
- Discontinuation of development of tipifarnib by the Sponsor.
- Request by a Health Authority.

Health Authorities and IRBs/IECs will be informed about the discontinuation of the study in accordance with applicable regulations. In the case of premature discontinuation of the study, the investigations scheduled for the End of Treatment assessment should be performed and the appropriate CRF section completed.

8.6 Definition of End of Study

For administrative and safety reporting purposes, the end of this clinical study is defined as 12 months from enrollment of the last enrolled study subject. If the last enrolled study subject discontinues treatment within 12 months of study enrollment, the End of Study will occur no

earlier than the date of the last enrolled subject's safety follow-up assessment performed approximately 30 days after treatment discontinuation (or until initiation of another anti-cancer therapy). At the time of End of Study, provisions will be made to transition all remaining study subjects who demonstrate sustained clinical benefit beyond the end of the study to other means of continued treatment with appropriate safety monitoring, e.g. single patient treatment protocol.

9 TREATMENTS

Subjects will receive tipifarnib as monotherapy in this study. In the absence of unmanageable toxicities, subjects may continue to receive tipifarnib treatment until disease progression. If a complete remission is observed, therapy with tipifarnib will be maintained for at least 6 months beyond the start of response.

Kura Oncology, Inc. or its designee will provide the study site with a supply of tipifarnib sufficient for the completion of the study.

All study subjects will be also eligible to receive best supportive care (BSC) defined as any standard supportive measures that are not considered a primary treatment of the disease under study. BSC will be provided by the study sites.

9.1 Investigational Product

Tipifarnib is a small molecule being developed as a potent, selective inhibitor of FTase for the treatment of cancer and other malignancies.

9.1.1 Product Characteristics

Tipifarnib film-coated tablets for oral administration are supplied in HDPE bottles. Two strengths (100 mg and 300 mg) of tablets are provided containing either 100 or 300 mg of Tipifarnib active substance, respectively. In addition to the active substance, the tablets contain the following inactive ingredients: lactose monohydrate, maize starch, hypromellose, microcrystalline cellulose, crospovidone, colloidal anhydrous silica, and magnesium stearate. The nonfunctional, taste-masking film coatings contain hypromellose, titanium dioxide, lactose monohydrate, polyethylene glycol, and triacetin. Each strength of tablet has the same excipients but the quantitative composition is slightly different. Further information can be obtained from the current version of the Investigator's Brochure.

9.1.2 Storage and Labeling

At a minimum, the label of each bottle of tipifarnib tablets shipped to the study sites will provide the following information: batch number/lot number, study identification, required storage conditions, directions for use, and country specific required caution statements (including "New Drug – Limited by United States federal law to investigational use" language).

Tipifarnib accountability records will be maintained by the pharmacy or designated drug preparation area at the study sites. Upon receipt of tipifarnib supplies, the pharmacist or designated study site investigational drug handler will inventory tipifarnib (separately for each strength, if applicable) and complete the designated section of the shipping form. The shipping/inventory form must be sent to Kura Oncology, Inc. or its designee, as instructed.

Tipifarnib should be stored at controlled room temperature 15 to 30 C (59 to 86 F). All study supplies must be kept in a restricted access area.

9.2 Treatment Administration

Tipifarnib will be administered orally, with food to each subject according to one of the following dose regimens:

- Regimen 1: 600 mg bid for 7 days on Days 1-7 in 28 day cycles (i.e. 1 week on / 3 weeks off).
- Regimen 2: 300 mg bid for 21 days on Days 1-21 in 28 day cycles (i.e. 3 weeks on / 1 week off).

On Day 1 of Cycle 1, only 1 dose of tipifarnib will be administered and will take place in the evening. Thereafter, tipifarnib will be administered orally with a meal in the mornings and again approximately 12 hours later, at approximately the same times each treatment day. Tablets should be swallowed whole with water (~8 oz. or 250 mL), but may be chewed or crushed if the Investigator deems it necessary.

Subjects may use proton pump inhibitors or H2 antagonists during the treatment portion of this study. However, subjects should be instructed to use antacids (magnesium or aluminum containing products) at least 2 hours before or after intake of oral study drug.

On Cycle 1 Day 1, the study site will provide tipifarnib to the subject from bulk supplies. Subjects will be provided with diaries with instructions to record the date and time of each dose and asked to bring the diaries and tablet bottles to each clinic visit for subject compliance and drug accountability review by the site staff.

9.3 Treatment Assignment

Treatment will be conducted in an open label manner and subjects will be randomized to one of the dose regimens to be evaluated in this study (as outlined in Section 9.2). Kura Oncology, Inc or its designee will assign a subject number identifier for each subject that is enrolled into the study. Study sites cannot enroll or start dosing the subject without receiving the assigned subject number.

9.4 Dose Selection

This study will evaluate two dose regimens: 600 mg administered bid on Days 1-7 of 28 day treatment cycles with the possibility to dose escalate to 800 mg bid, or to dose reduce to 400 or 200 mg bid, and 300 mg administered bid on Days 1-21 of 28 day treatment cycles with the possibility to dose reduce to 200 or 100 mg bid in order to support optimal dose selection for further clinical studies in subjects with MDS who are RBC transfusion dependent.

In the majority of its phase 2 program, tipifarnib was given orally at a dose of 300 mg bid for 21 days, followed by 1 week of rest, in 28 day treatment cycles (3 weeks on/1 week off schedule). Prior studies have shown that

those shown to demonstrate anti-tumor activity in preclinical tumor models. In a multicenter, phase 2 study in higher risk MDS patients (INT-28, N = 82), in which tipifarnib 300 mg bid was administered on the 3 weeks on/1 week off schedule, the response rate (CR + CRp + PR) was 15.9% and did not meet prespecified criteria (30% in order to reject null hypothesis) to support continued development in MDS using 300 mg bid 3 weeks on/1 week off. The most frequently reported hematologic AEs were thrombocytopenia (41%), anemia (34%), and granulocytopenia (29%). The most frequently reported non-hematologic AEs were fatigue (51%), diarrhea (38%), nausea (37%), and rash (24%). The observed safety profile in MDS patients was broadly similar to the other patient populations in which tipifarnib has been tested. For further details, please refer to the Investigator's Brochure.

However, given the underlying cytopenias often observed in patients with MDS, consideration was made for exploring alternative regimens that have been associated with less myelosuppression. The effect of higher dose levels given at intermittent schedules was tested in several clinical studies, including two trials in MDS and AML patients investigating alternate week dosing (7-day bid dosing followed by 7-day rest).

An alternate week dose regimen (bid days 1 – 7, and days 15 – 21 of a 28 day cycle) was investigated in 63 MDS patients. Sixteen of 61 (26%) evaluable patients responded (3 complete remissions and 13 hematologic improvements) with major platelet responses being most common (11 of 16 responders). The most common toxicity was myelosuppression (60% of patients). Twenty percent of patients had no side effects. Non-hematologic toxicities included fatigue (20%), skin rash (9%), diarrhea (16%), increase in liver transaminases (14%) and bilirubin (11%), and nausea (11%). DLTs of ataxia (n = 1), fatigue (n = 1), nausea (n = 1), and neutropenic fever (n = 2) occurred at tipifarnib doses above 1,200 mg/d. Alternate-week tipifarnib was concluded to be active and well tolerated at doses up to and including 600 mg orally twice daily (Kurzrock 2008).

Additionally, the alternate week schedule was evaluated in patients with relapsed/refractory AML at doses up to 1600 mg bid. At the 400 mg bid dose level, a grade 5 hepatorenal failure occurred, potentially related to the study drug. There were no additional DLTs reported at 600, 800 or 1000 mg bid dose levels. At the 1200 mg bid dose level, a grade 3 creatinine elevation

was seen in one patient out of 6 treated. At the 1400 mg bid dose level, one patient experienced a grade 4 hypotension and a rising grade 2 creatinine that were dose limiting, and a second patient had a rising grade 2 creatinine that resulted in treatment discontinuation and was therefore considered dose limiting. At the 1600 mg dose level, grade 3 liver function tests and a rising grade 2 creatinine were dose limiting, and in a second patient, a rapidly rising creatinine was seen and treatment stopped. As a result, the 1200 mg bid dose was established as the MTD and 7 additional patients treated. Sixteen patients were treated at the 1000 and 1200 mg dosing levels, with 3 of them experiencing complete responses. No formal responses were seen among patients treated at the lower dose levels (Kirschbaum 2011).

amendment 1. Additionally, intra-patient dose escalation to 800 mg bid is allowed at the discretion of the investigator if the subject has not experienced dose limiting toxicities at the 600 mg dose level. Subjects are not to be dose escalated until after completing Cycle 1 to ensure the dosing regimen is tolerated prior to escalation.

[figure not shown]
Upon review of the first 9 subjects enrolled in the study, the investigators noted that the alternative week regimen may not provide sufficient recovery time in subjects who experience myelosuppressive effects of tipifarnib. Therefore, the protocol was amended (Amendment 2) to adjust the treatment administration schedule to bid on Days 1-7 of 28 day treatment cycles. The investigators considered that by adjusting the dose regimen to allow for a 3 week rest period following each week of dosing, the myelosuppressive effects will be mitigated allowing subjects to make gains on increasing the cell counts as the cycles progress. Additionally, given the prior experience and tolerability with 300 mg bid on Days 1-21 of 28 day treatment cycles, this regimen was incorporated into Amendment 2 to support dose selection in future clinical studies.

[figure not shown]
Both dose regimens are expected to be well tolerated and to potentially provide clinical benefit to subjects with MDS. Furthermore, the current study allows for step-wise 100 - 200 mg dose adjustment based on subject tolerability. The data obtained from this study will be used to select the optimal dose and dose regimen to support the further development of tipifarnib in subjects with MDS

9.6 Treatment of Overdose

An overdose is defined as any dose greater than 30% over the daily tipifarnib dose. Any overdose must be recorded in the study medication and adverse event sections of the CRF. There is no known antidote for tipifarnib. In the event of overdose of tipifarnib, subjects should receive appropriate advice and supportive medical care by the Investigator or his/her designee and be followed-up accordingly.

For monitoring purposes, any case of overdose – whether or not associated with an AE (serious or non-serious) – must be reported to the Sponsor in an expedited manner.

9.7 Blinding

This is an open label study with no placebo or comparators.

9.8 Treatment Compliance

The importance of treatment compliance should be emphasized to the subject. Subjects will be given study drug and detailed instructions on how to take medications at home. Subjects will be instructed to return all used and unused study drug containers at each study visit. Subject compliance with the dosing schedule will be assessed by reconciliation of the used and unused study drug at each clinic visit and review of the dosing diaries. The quantity dispensed, returned, used, lost, etc. must be recorded on the dispensing log provided.

Compliance will be monitored and documented by site personnel on the appropriate form. The site personnel will question the subject regarding adherence to the dosing schedule by reviewing the dosing diaries, recording the number of tablets (and strengths, if applicable) returned, the date returned, and determining treatment compliance (at least 80% of the total assigned dose) before dispensing new medication to the study subject.

9.9 Investigational Product Accountability

The Investigator or designee is responsible for maintaining accurate records (including dates and quantities) of receipt of investigational product (IP), subjects to whom IP is dispensed (subject by subject specific accounting), and loss or accidental or deliberate destruction of IP.

9.10 Return and Disposition of Clinical Supplies

Unused tablets returned by the subject from a prior cycle of treatment may be re-dispensed to the subject. Study drug must be kept in a secure location for accountability and reconciliation by the Sponsor's designated clinical study monitor. The Investigator or designee must provide an explanation for any destroyed or missing study drug or study materials.

Study drug may be destroyed on site, per the site's standard operating procedures, but only after the Sponsor or its designee has been notified and granted approval for drug destruction. All study drug destroyed on site must be documented.

Documentation must be provided to the Sponsor or its designee and retained in the Investigator's study files. If a site is unable to destroy study drug appropriately, the site can return unused study drug to the Sponsor or its designee upon request. The return of study drug or study drug materials must be accounted for on a form provided by the Sponsor or its designee.

All study drug and related materials should be stored, inventoried, reconciled, and destroyed or returned according to applicable state and federal regulations and study procedures.

9.11 Prior and Concomitant Medications

All prescription and over-the-counter medications taken by a subject within 28 days before the first study drug administration will be recorded in the CRF. In particular, subjects will be asked about the use of agents that may affect the mevalonate pathway including statins (e.g. atorvastatin, simvastatin, rosuvastatin, pravastatin), bisphosphonates (e.g. pamidronate, risedronate, ibandronate, etidronate, alendronate) and nutritional agents (e.g. coenzyme Q_{10} , ubiquinone). Any additional concomitant therapy that becomes necessary during the study and any change to concomitant drugs must be recorded in the corresponding section of the CRF, noting the name, dose, duration and indication of each drug.

Supportive care medications considered necessary for the subject's safety and well-being may be given at the discretion of the Investigator according to local guidelines and standard practices. For concomitant therapy given as a treatment for a new condition or a worsening of an existing condition, the condition must be reported on the AE form of the CRF.

Subjects may use proton pump inhibitors or H2 antagonists during the treatment portion of this study. However, subjects should be instructed to use antacids (magnesium or aluminum containing products) at least 2 hours before or after intake of oral study drug.

Corticosteroids (up to 10 mg prednisone daily or its equivalent) may be administered for concomitant medical conditions.

Any additional concomitant therapy that becomes necessary during the study and any change to concomitant drugs must be recorded in the corresponding section of the CRF, noting the name, dose, duration and indication of each drug.

9.12 Non-permitted Treatments

Use of the following medications and therapies is not allowed during the study:

- Investigational agents other than tipifarnib.
- Any other anticancer therapy, including radiation or surgery, for the primary disease under study.
- Anti-apoptotic agents (e.g. amifostine) or immunosuppressive drugs (e.g. cyclosporine A, ATG).
- Corticosteroids > 10 mg prednisone daily or its equivalent
- Subjects should not use enzyme-inducing anti-convulsants (e.g. phenytoin, phenobarbital, and carbamazepine) while taking tipifarnib. If needed, subjects may use non-enzyme-inducing anti-convulsants (e.g. gabapentin, topiramate, valproate) while taking tipifarnib.

If the administration of a non-permitted concomitant drug becomes necessary during the study, e.g. because of AEs or disease progression, the subject in question will be withdrawn from the study, and the subject's data obtained before the withdrawal may be used for safety and efficacy evaluations.

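### Protocol 9.12 removes a subject who needs a non-permitted drug from the study rather than from treatment, which can end PFS, duration-of-response and survival follow-up before progression (minor)

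*Protocol*

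**What the plan says.** Protocol 9.12 lists non-permitted treatments. Some are directed at the disease (other anticancer therapy, investigational agents). Others are not, for example "Corticosteroids > 10 mg prednisone daily or its equivalent"; 9.11 sets the matching limit: "Corticosteroids (up to 10 mg prednisone daily or its equivalent) may be administered for concomitant medical conditions". If a listed drug is needed, "e.g. because of AEs or disease progression", then "the subject in question will be withdrawn from the study". The only statement about data is that the subject's "data obtained before the withdrawal may be used for safety and efficacy evaluations".

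Protocol 8.4 handles the same event differently. It says "the reasons for which the Investigator or Kura Oncology may withdraw a subject from study treatment include", among others, "Subject requires or has taken medication prohibited by the protocol". Separately, it provides that a subject's "participation in the study may also be discontinued at any time at the discretion of the Investigator".

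Protocol 8.1 and 10.1, the Synopsis and SAP 4.1 say what happens to subjects who stop treatment alive and without progression. They have disease assessments about every 12 weeks and monthly blood counts until one of three events: progression, withdrawal of consent to procedures, or the start of other anticancer treatment. Section 11.6.1 and Table 1 footnotes 4, 17 and 24 give the visits. Survival contact (11.6.2, Table 1 footnote 5) begins at progression. SAP 7.5 censors dropouts who have no event.

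**The concern.** The two sections differ in scope (study against treatment) and in force (a rule against an option). A site can follow either with protocol text in support, so two identical subjects could be followed for very different lengths of time.

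The case that matters is a subject without progression who receives a listed drug that is not anticancer therapy. None of the three stopping events in 8.1 has occurred, so the plan wants assessments to go on; 9.12 read literally stops them. Because survival contact starts only at progression, a subject removed earlier never reaches it. PFS, duration of response and 1-year survival would then be censored at removal. Section 9.12 names adverse events as a trigger, so this censoring may be related to prognosis, whereas Kaplan-Meier estimation assumes that it is not.

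**Working it through.** **1. The sections applied to one subject.** Suppose a subject without progression needs prednisone above 10 mg daily for an adverse event.

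| Section | Consequence |
|---|---|
| 9.12 | Mandatory withdrawal from the study; only earlier data are mentioned |
| 8.4 | Possible withdrawal from study treatment |
| 8.1, 10.1, 11.6.1 | Disease assessments and monthly counts continue, since no stopping event has occurred |
| 11.6.2 | Not reached, because there is no progression |
| SAP 7.5 | Censored if the subject drops out without an event |

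The first and third rows cannot both be followed. Corticosteroids are the cleaner example: the restriction on enzyme-inducing anticonvulsants applies only while the subject takes tipifarnib.

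**2. What one such subject can lose in year 1.** Inputs: disease assessments about every 12 weeks, taken here as weeks 12, 24, 36 and 48 (consistent with the roughly 4 intervals per year in Protocol 12.2.1); required marrows in Cycles 3, 6 and 9; monthly counts; an End of Treatment visit about 30 days (30/7 = 4.3 weeks) after the last dose. One month = 52/12 = 4.33 weeks. The last column assumes that the last dose falls at withdrawal.

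| Withdrawal just after | Assessments lost | Marrows lost | Time left to week 52 | Time left after End of Treatment visit |
|---|---|---|---|---|
| Week 12 | 4 − 1 = 3 of 4 | 3 − 1 = 2 of 3 | 40 wk / 4.33 = 9.2 months | 40 − 4.3 = 35.7 wk = 8.2 months |
| Week 24 | 4 − 2 = 2 of 4 | 3 − 2 = 1 of 3 | 28 wk = 6.5 months | 23.7 wk = 5.5 months |
| Week 36 | 4 − 3 = 1 of 4 | 3 − 3 = 0 of 3 | 16 wk = 3.7 months | 11.7 wk = 2.7 months |

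These are close to upper limits. They assume removal just after a visit and a subject who would otherwise have stayed alive, progression-free and off other anticancer therapy to week 52. Section 8.4 asks for the End of Treatment tests where possible. Under 11.5 that visit includes a response assessment, and a marrow if it falls within the first 9 months. In the week 36 row it would fall at about 36 + 4.3 = 40.3 weeks = 9.3 months, so no marrow would be required. Set off one for one against the losses, that visit leaves a shortfall of 2, 1 and 0 assessments and 1, 0 and 0 marrows.

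**3. The decision rules.** The design's own figures reproduce. With stage 1 continuing at 2 or more of 11 and success at 4 or more of 18,

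P(success) = Σ over x = 2 to 11 of Bin(x; 11, p) × P(Bin(7, p) ≥ 4 − x).

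This gives 0.0875 at p = 0.10 (stated 0.087) and 0.8001 at p = 0.30 (stated 80%). The stage 1 stopping probabilities are 0.6974 and 0.1130 (stated 0.697 and 0.113). Nothing in this point disputes these figures.

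**4. If only the withdrawal wording is changed.** The 9.12 list includes ATG and cyclosporine. Protocol 5.4 describes both as treatments evaluated in MDS, and 5.6 regards immunosuppression as active there. ORR is a best overall response that includes hematologic improvement (Protocol 12.2.1, SAP 9.1), with no cut-off at a prohibited drug. Duration of response is censored only for non-protocol anticancer treatment (SAP 9.2). Unless ATG or cyclosporine is classed as anticancer therapy, which the documents do not settle, an improvement after either could count towards the 2 of 11 and 4 of 18 rules. Continued follow-up therefore needs a data rule.

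**The case against.** The strongest reply is that the rest of the plan largely settles the matter. Section 8.4 is the dedicated removal section and SAP 4.2.2 points to it. The follow-up rule appears in several places, and 9.12 never says in terms that assessments stop. The harm arises only at a site that reads 9.12 literally. The group is narrow, and duration of response is affected only if the subject has responded. All of this stands and keeps the point minor. It does not remove the conflict, because 9.12 is the specific rule for this event and is worded as mandatory. The investigator's discretion in 8.4 does not help either: it is case by case, whereas 9.12 makes removal automatic.

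Four stronger readings are tempting, and the documents do not support them.

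- *The ORR test loses power.* No share of missed responses is given, and the End of Treatment visit includes a response assessment. A power figure would rest on an invented input.
- *Subjects who start other therapy at progression are lost to survival follow-up.* The wording of 9.12 does clash with 11.6.2, but the rule to follow all subjects for survival after progression is repeated in 8.1, 10.1, 11.6.2, Table 1 and SAP 4.1, so loss is less likely. The point does not rest on that case.
- *Section 8.4 defines removal from the study as the end of data collection.* That paragraph concerns a subject who withdraws permission to use health information; collection stops for that reason.
- *A wording change alone is enough.* Step 4 of the working shows why the SAP also needs a sentence.

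**Conclusion.** The inconsistency is real and minor. For a subject without progression who is given a listed non-anticancer drug, 9.12 read literally ends PFS, duration-of-response and survival follow-up early, and the resulting censoring may be informative. The effect is confined to secondary endpoints that carry no decision rule. Its size in any estimate cannot be computed, because the number of such subjects is unknown. Per subject, the loss is at most 3 of 4 year-1 assessments and 2 of 3 marrows, less what the End of Treatment visit supplies. The conclusion assumes that a site applies 9.12 as written and takes withdrawal from the study to end assessments; that is an inference from its wording, not an explicit instruction.

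**What to change.** In Protocol 9.12, change the withdrawal from one out of the study to one out of study treatment. Add that the subject continues follow-up for safety, progression and survival under 8.1, 11.5 and 11.6 unless consent is withdrawn. The investigator's discretion in 8.4 stays as it is.

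Keep a data rule, stated in 9.12 and in SAP 9.1 and 9.2. A response first documented after the start of a non-permitted drug with potential activity in MDS (other anticancer or investigational agents, or immunosuppressants such as ATG or cyclosporine) does not count towards ORR, and duration of response is censored at the start of that drug.

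The cost is a short edit to 9.12, one added SAP sentence, and a few more visits or calls for these subjects, all of which are already in Table 1.
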